### Physician data regarding disease activity including physical examination

Physicians will fill in all the information necessary to calculate the following composite scores: DAPSA remission, DAPSA Low Disease Activity (using both DAPSA and c-DAPSA), PASDAS remission, AMDF modified remission, MDA and its several versions including MDA where both joint measures are mandated, MDA where the skin measure is mandated, MDA where these three are mandated and Very Low Disease Activity (VLDA) corresponding to all MDA criteria fulfilled. (Schoels 2015, Smolen2015, Mumtaz2011, Helliwell2014, Coates2010, Coates2016a, Coates2016d)

This includes a physical assessment with 66 swollen joint counts, 68 tender joint counts, tender enthesal points (Leeds Enthesitis Index), body surface area of psoriasis and physician global assessment. Weight and height will also be collected.

Physicians will also answer general questions on their gestalt on the disease status (remission/low disease activity or flare, please see above). To better understand the reasoning of the physician, specific questions related to the perceived cause of current symptom levels will also be asked: causality of patient symptoms between disease activity, sequels of disease or comorbidities. (as was the case in a recently-completed study in spondyloarthritis, Dougados 2017)

Here we are using a modified AMDF with no PASI replaced with skin global assessment and body surface area, to facilitate feasibility of data collection in rheumatology clinics. Furthermore the PsA Quality of Life score which is part of AMDF will not be collected: thus this is a modified AMDF. (McKenna2004, Mease2016)

We are aware we will not be collecting the data needed to calculate the Composite Psoriatic Disease Activity Index (CPDAI) for feasibility reasons. However a modified CPDAI may be calculated based on available data.

We will avoid circularity by not calculating the composite scores in the CRF.

### Blood test results

No specific blood tests will be performed for this study.

The last available results (<4 weeks) for C Reactive Protein will be collected in the CRF and when answering the CASPAR criteria questions, the physician will be asked for Rheumatoid Factor test results (in the patient's lifetime).

### Radiographic assessment

The last available X-Rays of hands and feet will be assessed locally by the health professional to answer the CASPAR question on the presence or not of specific radiographic changes.

### Treatment changes

Physicians will collect patient treatments for PsA and will answer if the treatment is changed or not and in which way (i.e., intensification, yes/no) at each visit.

## Patient CRF (Table 1)

### General questions

Question regarding demographic data and smoking status as well as current levels of physical exercise will be asked.

### Elaboration of the patient questions for remission/ flare

For these questions, flare and remission/low disease activity questions were developed for the purpose of this study. Patients will answer a specific targeted question on their assessment of remission yes/no and low disease activity yes/no. These unique and binary questions were refined with our 4 patient research partners because none exist in PsA. For flares also, we developed a binary question with the patient partners: using as basis the GRAPPA Flare pivotal question as well as previous work in the field of rheumatoid arthritis (Moverley 2016, Alten2011, Bykerk2016)

The questions were elaborated in a teleconference in March 2017 with the 4 patient research partners with PsA. The goal was to elaborate a global question for remission, and for low disease activity, and a global question for flare. A translation of the flare/ remission/low disease activity questions will be performed by 2 persons.

### Patient generated data regarding disease activity

PROs will be collected for PsA patients, at baseline and 1-6 months later at the second visit. Given difficulties with international authorizations for online data collection, the data will be collected anonymously in paper format.

#### *Remission assessment*

The Patient Acceptable Symptom State (PASS) will be assessed: this corresponds to the clinically relevant cut-off from the patient's perspective allowing classification of patients as being in « an acceptable state » or not with one question ("If you were to remain for the rest of your life as you were during the last 48 hours, would this be acceptable or unacceptable for you?"). (Tubach2012, Wariaghli2012) The PASS will be collected at baseline and at the second visit. (Heiberg2008, Tubach2012)

Patients will also answer a specific targeted question on their assessment of remission yes/no and of low disease activity (please see above).

#### *Flare*

Only flares at the time of assessment are targeted (and not recall of previous flares).

To assess flares from the patient perspective, the preliminary GRAPPA flare instrument will be evaluated: 1.A recent change in joint pain.2.A recent change in location of symptoms (i.e., sudden increase in pain or swelling in hands/feet).3.A recent change in the number of tender and/or sore joints. 4. A recent change in the

number of aching joints. 5. The presence or degree of pressure-sensitive joints. 6. A recent change/increase in the number of swollen joints. 7. A recent change/increase in night pain. 8. A recent change/increase in the number or combination of symptoms (**Table 1**). (Moverly2016a)

Patient will also answer a specific targeted question on their assessment of flare yes/no (see above).

The Minimum Clinically Important Difference (MCID) question gives information on change in disease status. The question is: "How would you describe your overall status since your last visit: much better, better, the same, worse, much worse?" Here, worse or much worse will be used to define a flare. (Curtis2015)

### *Composite PROs*

The PsAID is a questionnaire that can be used to calculate a score reflecting the impact of psoriatic arthritis (PsA) from the patients' perspective. (Gossec2014e)

The 12-Item Short Form Health Survey (SF12) is a multi-purpose, generic health survey. (SF36 online) It yields an 8-scale profile of functional health and well-being scores as well as psychometrically-based physical and mental health summary measures and a preference-based health utility index. A physical summary score (physical composite score: PCS) and a mental summary (mental composite score: MCS) are calculated according to an established algorithm. PCS includes physical function, physical role, bodily pain and general health and MCS includes mental health, emotional role, social function and vitality. The SF-12 is copyrighted. It can be used instead of SF-36 in composite scores, as recently proposed.

### *Unidimensional PROs*

Patient Global Assessment (PGA) (on a 0–10 scale) asks the patient to give an overall assessment of how the arthritis is doing, thereby integrating a number of dimensions related to disease activity or to other aspects. The wording of questions and anchors are usually as follows: for the PGA, 'Considering all of the ways your arthritis affects you, mark "X" on the scale for how well you are doing' ('very well' to 'very poor').

Patient global for skin and for joints will also be evaluated on a numeric scale from 0 to 10 since part of the AMDF. (Helliwell2013) This will also give some indication on patient-perceived skin involvement.

Pain will be evaluated on a numeric scale from 0 to 10.

Fatigue will be analysed also (it is included in the PsAID).

The HAQ-Disability index is a disability questionnaire which includes 8 domains scored on a 0-3 scale (0 = without any difficulty, 1 = with some difficulty, 2 = with much difficulty, 3 = unable to do). (Pincus2007)

The validated single questions to define Minimal Clinically Important Difference (MCID) and PASS will be assessed as explained above.

## **CRF translations**

The physician CRF does not need to be translated. In the patient CRF, existing validated translations of the tools integrated in the CRF will be used. The rest of the CRF (i.e., demographic data etc) will only have a simple translation (by one person).

For the global remission and flare questions as well as for the Leeds Flare questionnaire, we need to perform translations since some of these questions were developed for this study (remission/flare questions) and the Leeds Flare questionnaire is not translated.

We will follow a simplified but validated translation and cross cultural adaptation process (Guillemin1993, Beaton2000).

Step 1: Two persons (at least 1 rheumatologist, at least one bilingual person, and wherever possible also a patient research partner) translate independently the English version into the target language.

Step 2 : consensus between the translators leads to a final version. Please keep in mind that the final wording needs to be understood by lay people including low-education people ("the aim is for a 9-yr old child to understand the wording").

Step 3: Backward translation of the new-language version into English is performed by an independent bilingual native English speaker, blinded to the English original version.

[figure not shown]
Step 4: consensus meeting between the translators to check the meaning has not been changed or lost. The group will compare the initial version and the back-translation and will discuss the phrasing of the target-language version, and by consensus will produce a final version. The committee has to ensure that the translation is fully comprehensive and to verify cross-cultural equivalence of the source and final versions. Please keep in mind again at this phase that the final wording needs to be understood by lay people including low-education people.

**Table 1: data collection**

Type of data	Collected data	Baseline	1-6 months
Patient CRF	Identifying initials and patient number	X	X
	Gender	X	
	Smoking status, height and weight	X	
	Exercise levels	X	
	Patient Pain Visual Analogue Score	X	X
	Patient VAS for skin	X	X
	Patient VAS for joints	X	X
	Patient's Global Assessment of Disease Activity	X	X
	Health Assessment Questionnaire	X	X
	SF-12	X	X
	PsAID-12	X	X
	Disease status: remission yes/no, low disease activity yes/no, flare yes/no, and number of recent flares	X	X
	MCID	X	X
	GRAPPA flare instrument	X	X
	PASS	X	X
Physician CRF	Year of birth of the patient	X	
	CASPAR criteria (individual criteria)	X	
	Confirmation of PsA by the physician	X	
	Year of PsA diagnosis	X	
	Treatments	X	X
	Level of studies	X	
	Physician Global Assessment	X	X
	Predominant type of PsA: axial, peripheral, enthesitic	X	
	Tender joint count (68)	X	X
	Swollen joint count (66) and deformed joints	X	X
	Body surface area of Psoriasis (%)	X	X
	Tender enthesal points (Leeds Enthesitis Index)	X	X
	CRP	X	X
	Comorbidity index (Groll2005)	X	
	Disease status: remission yes/no, low disease activity yes/no, flare yes/no, qualitative questions regarding cause of symptoms	X	X
	Treatment intensification (yes/no)	X	X

## Outcomes and planned analyses

Of note, as the concepts of remission and flare are not well defined and there is no gold standard, we have to 'go around' the concept using several partial gold standards. This explains the multiple analyses (**Figure**)..

# Assessment of levels of scores

\* Assessment of change in scores between the 2 visits

We plan to define cutoffs of the most widely used composite scores and PROs, for levels corresponding to remission/low disease activity and for changes in levels corresponding to flares, in PsA, when remission/low disease activity and flare are defined from the patient and physician perspective.

**To this end we will 'define' remission and flare as follows:**

**From the physicians' perspective**

-the main definition for 'remission' used here will be MDA

-and sensitivity analyses will use the treating physician-perceived remission or low disease (single questions), other definitions of MDA as recently proposed, and remission in composite scores (cutoffs have been defined for DAPSA, modified AMDF, PASDAS);

- for flare the gold standard will be decision of treatment intensification

-and sensitivity analyses will use: global assessment of flare and increase in category of disease activity in the composite scores.

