### **Obtaining cutoffs**

We will assess what physician-defined remission/low disease activity/flare and patient-defined remission/low disease activity/flare correspond to both on composite 'physician' scores and on all the collected PRO scores (**Figure and Table 2**). We will use data collected at baseline cross sectionally for remission and low disease activity and changes in scores between the 2 visits for flares.

We will use data collected at baseline and at 1-6 months since flare is usually referred to as a change in disease status and indeed we are planning to define cutoff values for change in each outcome, corresponding to a flare.(Gossec2016)

Although we are aware the cutoff values obtained may differ between physicians and patients, we are not planning a reconciliation exercise.

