### **Statistical analyses**

#### *Sample size*

The sample size is calculated to be able to determine the cutoff value of PsAID corresponding to remission or flare with a certain precision.

With a standard deviation of 2.30 as observed in the PsAID development study on 107 and 475 patients, with a confidence level of 0.95 and a precision of 0.05, it is necessary to analyse 82 patients in 'remission' (whatever the remission definition) or in flare. Since we expect around 20% of patients to be in remission in this usual practice cohort (given percentages of MDA are around 40-50% in randomised clinical trials of biological), and around 20% of patients to be in flare, we need to analyse a total of 410 patients for remission, thus we need to include 450 patients (taking into account uninterpretable CRFs due to missing data). (SAMPLE, Möttönen1999). For flares we are aware the sample size will be slightly smaller (taking into account patients having had a treatment intensification will not be assessed the second time), however for this exploratory analysis the sample size is considered sufficient for flares.

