### *Planned analyses*

Population: Analyses will be performed on all included patients with data available regarding the remission and flare status questions.

For remission, all included patients with data available regarding remission will be assessed. The primary analysis is on baseline data. The data from the second visit will be seen as confirmatory and will be analysed as longitudinal data accounting for multiple visits.

For flare, only patients with both visits completed will be used. Change in outcomes between the 2 visits will be assessed.

Similarly to what has been done in axial spondyloarthritis (and differently to what has been done in rheumatoid arthritis), it is decided that flare will be defined as a change in status between the 2 time points, i.e., a flare is an absolute or relative change between 2 values: the observed value of the outcome at the time of the flare, minus the referral value (previous status before the flare). (Gossec2016, Bykerk2016)

The patient's initial status (referral value of the outcomes at the first visit) may vary from no symptoms to moderate/high disease activity but we will analyse separately patients with very high initial values, since it is considered that definitions of flares are only relevant for patients initially not in very high disease activity.

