### Planned analyses:

Cutoff values for each outcome and for each change in outcome will be calculated using ROC curves and 75th percentile analyses (**Table 2 and 3**). For ROC curves, different cutoffs will be calculated, both using Youden's statistic (maximizing both sensitivity and specificity) but also using a fixed specificity number (80%) since specificity is more important than sensitivity in this case (to avoid overdiagnosing

flares). The 75th percentile technique is a classical technique which finds the value above which, 75% of patients reporting an outcome or a change in outcome, are placed. Rasch analysis will be used as appropriate. (Tubach2005, Machado2016) These techniques are widely used to determine cutoff values for continuous scores and are recommended by COSMIN (Mokkink2016/ website.cosmin)

Sensitivity analyses will explore cutoff values found according to patient demographic characteristics and country.

We will compare attainment of remission/low disease activity or flare according to the different definitions, using kappa analyses and logistic regression analyses will explore characteristics of patients who are in 'discordance' or not for flare/remission with the physician-defined definition, and physicians who are in 'discordance' with patients as well.

Missing data: All data will be analysed. To minimize missing data, the order of questions will also be studied to motivate respondents to finish the entire questionnaire.

**Table 2.** Planned analyses: defining cutoff values according to different definitions of remission/low disease activity (LDA)

Gold standards are below	MDA	Modified versions of MDA	Physician Gobal Assessment	DAPSA/c-DAPSA	PASDAS	Modified AMDF	PsAID	HAQ	Pain	Fatigue	PGA	SF12
MDA												
modified versions MDA												
Physician remission/LDA single questions												
Physician Global Assessment<4/10												
Composite score DAPSA												
Composite score PASDAS												
PASS												
Patient remission/LDA single questions												

**Table 3.** Planned analyses: defining cutoff values for change of outcomes according to different definitions of flare

Gold standards are below	MDA	Physician global ass.	DAPSA/c-DAPSA	PASDAS	Modified AMDF	GRAPPA flare questionnaire	PsAID	HAQ	Pain	Fatigue	PGA	SF12
Treatment intensification												
Physician flare single question												
Composite score DAPSA change in category												

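### The main physician flare reference does not require worsening, so patients intensified for persistent activity pull the 75th-percentile change cut-off toward or past zero; the visit that counts also needs stating.

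*Combined protocol and SAP*

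**What the plan says.** Under From the physicians' perspective, "for flare the gold standard will be decision of treatment intensification". The synopsis, long summary, Objectives and the flare table of planned analyses repeat this, and none adds a worsening condition. Treatment changes and Table 1 record intensification as yes or no at both visits.

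Obtaining cutoffs uses "changes in scores between the 2 visits for flares". The Planned analyses section states that "it is decided that flare will be defined as a change in status between the 2 time points", computed as the value at the flare minus the earlier value. It adds "For flare, only patients with both visits completed will be used" and "we will analyse separately patients with very high initial values", with no threshold for very high. The percentile method "finds the value above which, 75% of patients reporting an outcome or a change in outcome, are placed".

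Sample size calls the flare analysis exploratory and says "it is necessary to analyse 82 patients in 'remission' (whatever the remission definition) or in flare". It expects fewer patients for flare, "taking into account patients having had a treatment intensification will not be assessed the second time". Data collection says that every patient is assessed twice, and Budget expects 450 first and 400 second visits.

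**The concern.** The plan's concept of flare is a change in status, but the main physician reference is a treatment decision that can be taken without any change. Inclusion criteria admit patients at any level of activity, so some intensification decisions may be taken because activity has stayed up. Those patients count as flares with a change near zero.

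The percentile rule is the 25th percentile of change in the flare class, so it is sensitive to what sits in the lower tail. The result could be read as the worsening that physicians treat as flare while partly describing patients who did not worsen. That runs against the plan's stated wish to avoid overdiagnosing flares. Larger numbers would not remove the shift.

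The visit matters for the same reason. Patients intensified at baseline have their change measured after treatment was stepped up, and some would be expected to improve.

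**Working it through.** **The plan's own figure.** For 82 patients the formula is n = (1.96 × SD / d)². With SD 2.30 and the printed precision d = 0.05, n = 8,129. With d = 0.5, n = 82. The printed 0.05 is a separate matter. Here 82 serves only as the planned number of flares. From Budget and the 20% flare rate in Sample size, 0.20 × 400 = 80 flares can be expected to have a change score.

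**Inputs not in the documents (assumptions).** These are the share m of intensified patients who did not change, the mean change in true flares, and the SDs of change. Higher is taken as worse.
- Case A: true flares mean +2, SD 2; unchanged and non-flaring patients mean 0, SD 1.5.
- Case B: mean +3 against 0, SD 2.3 in both.

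**Percentile cut-off.** It is the c that solves (1 − m)Φ((c − μ)/σ) + mΦ(c/σ₀) = 0.25.
- At m = 0: A, 2 − 0.6745 × 2 = 0.65; B, 3 − 0.6745 × 2.3 = 1.45.
- Check at m = 0.20 in A, c = 0.15: 0.8 × Φ(−0.925) + 0.2 × Φ(0.10) = 0.142 + 0.108 = 0.25.

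| Unchanged | 0% | 5% | 10% | 15% | 20% |
|---|---|---|---|---|---|
| Cut-off, A | 0.65 | 0.52 | 0.39 | 0.27 | 0.15 |
| Cut-off, B | 1.45 | 1.27 | 1.08 | 0.89 | 0.69 |

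The shift at 20% is 0.50 (A) or 0.76 (B). At 30% in case A the cut-off is −0.07, so a patient with no change would count as a flare. The proportion of non-flaring patients above the cut-off rises from 33% to 46% (A) and from 26% to 38% (B) between 0% and 20% unchanged. Other assumed values (mean change 1.5 to 3, SD of change 1.78 or 2.30) gave shifts of about 0.35 to 0.78 at 20%, always in the same direction.

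**Against sampling error.** SE = √(0.25 × 0.75 / n) / density at c. With n = 80 and no unchanged patients, the 95% half-width is 0.60 (A) or 0.69 (B). The shift at 20% is of that order, but does not shrink as n grows.

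**ROC cut-offs.** If non-cases have the same distribution as the unchanged patients, sensitivity + specificity − 1 equals (1 − m) times its value at m = 0. The Youden cut-off therefore stays at 1.26 (A) or 1.50 (B). The 80%-specificity cut-off depends on non-cases alone: 0.8416 × σ₀ = 1.26 or 1.94. Only apparent sensitivity at that cut-off falls at 20% unchanged, from 0.64 to 0.56 (A) and from 0.68 to 0.58 (B).

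**Would restricting to labelled worsening be better?** Root mean square error (RMSE) around the true-flare value, starting from 80 intensified patients, under two labelling assumptions:
- Label independent of the size of change, given to 80% of true flares and to no unchanged patient. At 20% unchanged, 80 × 0.8 × 0.8 = 51 patients remain. RMSE for all intensified against restricted is 0.59 v 0.38 (A) and 0.86 v 0.44 (B). Restriction wins above 6.4% (A) or 4.5% (B) unchanged.
- Label more likely with larger change, P(label) = Φ(change/2). The restricted cut-off overshoots: 1.21 (A) or 1.94 (B) at 10% unchanged, and 1.04 or 1.76 at 20%. RMSE at 10% is 0.40 v 0.64 (A) and 0.53 v 0.60 (B). At 20% it is 0.59 v 0.50 and 0.86 v 0.48. Restriction wins only above about 17% (A) or 12% (B).

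**The visit.** The change formula needs a flare at visit 2, and the Flare section targets only flares present at assessment. Both point to the second-visit decision. But intensification is recorded at both visits with no statement of which one counts. The Sample size remark fits only a baseline intensification, and it conflicts with Data collection. Budget expects 450 − 400 = 50 missing second visits (11%) for all reasons. The documents give no baseline intensification rate to set against that. If baseline decisions were counted and those patients improved by 1 point on average (assumed; flares +2, SD 2.30), a 20% share would move the cut-off from 0.45 to −0.31.

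**The case against.** The choice is disclosed. Background calls intensification a surrogate, and Outcomes and planned analyses says that several partial gold standards are used because none exists. The physician flare question has its own row in the flare table, so a cut-off for physician-labelled flare will appear anyway. Very high initial values are analysed separately, and those patients are the likeliest to be intensified without worsening. The flare analysis is exploratory.

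All of this stands and limits the weight of the point. It does not show how far the main percentile cut-off is diluted. The separate row uses a different set of patients, very high has no threshold, and moderately active patients remain.

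Three stronger readings are tempting, and the documents do not support them.
- A reader might infer that all the flare cut-offs are biased; the two ROC cut-offs are not if non-cases are stable.
- A reader might infer that the plan gives no indication of the visit, or that intensified patients can have no change score. The change formula implies visit 2; what is missing is an explicit statement and a reconciled Sample size remark.
- A reader might infer that the restricted cut-off should replace the planned one. Whether that helps depends on a share the documents do not give and on how the flare label is assigned.

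**Conclusion.** The point holds in a limited form. The main physician reference omits the change by which the plan defines flare, and unchanged patients move the percentile cut-off toward or past zero. The direction is firm provided that some intensified patients are unchanged. The size is not: 0.50 to 0.76 points at 20% unchanged rests on assumed shares, means and SDs. For SF-12, where higher is better, the sign reverses.

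One of three cut-off methods is affected, for one main reference, in an exploratory analysis. This is a worthwhile, cheap improvement and does not invalidate the flare analysis. Replacing the planned cut-off is a trade-off that the evidence does not settle. Separately, the statements about the second assessment of intensified patients contradict each other and need reconciling.

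**What to change.** 1. State that the intensification decision at the second visit defines the physician flare. Reconcile the Sample size remark with Data collection, Planned analyses and Budget.
2. Keep the percentile cut-off for all intensified patients as planned. Beside it, report the share of intensified patients without physician-reported flare at visit 2, and the percentile cut-off among intensified patients whose physician answered yes to flare at visit 2. Give each its number of patients and 95% interval.
3. Read the two cut-offs as a likely range, and do not present the all-intensified value alone as the worsening that physicians treat as flare. The range is not guaranteed: if 10% of unchanged patients are also labelled (with 80% of true flares labelled), the restricted cut-off at 20% unchanged is 0.57 (A) or 1.34 (B), slightly short of 0.65 and 1.45.

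Do not use the MCID answer as the condition, because it is a patient reference and the plan keeps the two perspectives apart. Do not use an increase in composite category, because it is built from scores being cut. The ROC cut-offs and the patient references stay as planned.

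The cost is a text change and a little more analysis; Table 1 already collects the items at both visits. The subgroup is smaller: with true flares only, the 95% half-width grows from 0.60 at 80 patients to 0.69 at 60 and 0.84 at 40 (A), or from 0.69 to 0.79 and 0.97 (B). The restricted value may overshoot if the label depends on the size of change.

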**There are several definitions of remission and acceptable residual disease activity levels in PsA.** (Kavanaugh2006, Acosta2014) The Group for Assessment of Psoriasis and Psoriatic Arthritis (GRAPPA) suggested that remission in PsA should be characterized by “a complete absence of disease activity, with no signs or symptoms of active disease”. (Kavanaugh2006) In parallel, the European League Against Rheumatism (EULAR) defined remission in PsA as “the absence of clinical and laboratory evidence of significant inflammatory disease activity.” (Gossec2016a) Contrary to the situation in rheumatoid arthritis where a specific definition of remission has been proposed by a European League Against Rheumatism (EULAR)/American College of Rheumatology (ACR) consensus (Aletaha2010a, Bykerk2012), in PsA a specific and quantifiable definition of remission is lacking. However some approaches have been proposed recently based on physician consensus exercises and using composite disease activity scores. Remission and low disease activity definitions have been defined using the Disease Activity index for Psoriatic Arthritis (DAPSA) (Aletaha2016b) The DAPSA is composed of five untransformed, unweighted variables, including two patient-centered items (patient global assessment and pain on an 11-point numeric rating scale), one physician centered item (swollen joint count using 66 joints, 66-SJC), one item dependent on patient and physician (tender joint count using 68 joints, 68-TJC), and a laboratory variable (C Reactive Protein (CRP) in mg/dL). (Aletaha2016b) The DAPSA-based remission status (i.e., a score <4 points) is associated with no or minimal residual ultrasound signals in the joints. (Schoels2016) A clinical DAPSA score (c-DAPSA) is also available and is calculated using the same variables as DAPSA, without CRP. Other measures with validated definitions of remission include the Composite Psoriatic Disease Activity Index (CPDAI), the GRAPPA-developed PsA Disease Activity Score (PASDAS) and Arythmetic Mean of Desirability Functions (AMDF). (Mumtazz2011, Helliwell2014)

An alternative treatment target is Minimal Disease Activity (MDA). Minimal disease activity (MDA), agreed at the Outcome Measures in Rheumatology Clinical

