Composite score PASDAS change in category												
GRAPPA flare questionnaire												
Patient flare single question												
Worsening MCID												

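### In Table 3's two category-change rows (DAPSA, PASDAS), the flare anchor is computed from the outcome itself, so the same-score cells look accurate without any flare

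*Combined protocol and SAP*

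**What the plan says.** Under the physicians' perspective in Outcomes and planned analyses, the main rule is "for flare the gold standard will be decision of treatment intensification". The sensitivity definitions are "global assessment of flare and increase in category of disease activity in the composite scores".

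Table 3 turns the second of these into two of its seven anchor rows: "Composite score DAPSA change in category" and "Composite score PASDAS change in category". Its columns include DAPSA/c-DAPSA, PASDAS, pain and PGA. The Background describes the DAPSA as an unweighted five-item sum, "including two patient-centered items (patient global assessment and pain on an 11-point numeric rating scale"; the other items are the two joint counts and CRP. It gives one category boundary: "The DAPSA-based remission status (i.e., a score <4 points". The documents do not give the other DAPSA boundaries, the PASDAS boundaries or the PASDAS items.

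The outcome set against each anchor is the visit-2 minus visit-1 difference: "a flare is an absolute or relative change between 2 values" (Statistical analyses, Planned analyses). Cutoffs come from ROC curves (Youden, and specificity fixed at 80%) and the 75th-percentile method. Obtaining cutoffs seeks them on the composite scores and on every patient-reported score, without exception.

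**The concern.** A category rise depends on where the patient starts as well as on how much the patient worsens. A DAPSA moving from 3.5 to 4.5 crosses the documented boundary on a 1-point rise and counts as a flare. If the next boundary were 14 (an assumption), a move from 5 to 13, a rise of 8, would not count. A patient starting in the top category cannot rise at all.

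The larger problem is circularity. In the DAPSA row and DAPSA column, the two visit values decide both whether the patient is a flare and how large the change is. An unusually high second reading produces both. Pain and PGA inherit part of this because they are summed into the DAPSA.

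A sensitivity analysis is useful only if it can disagree with the main result. The same-score cells return high accuracy whether or not anyone flares, so agreement with the treatment-intensification cutoffs would say little. The plan also ranks specificity above sensitivity so as not to overdiagnose flares, and an anchor that fires on noise works against that aim.

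**Working it through.** The plan gives no false-firing rate or accuracy for this anchor, so there is no figure to reproduce. Its nearest numbers are an expected 20% in flare (Sample size) and 400 second visits (Budget): 0.20 × 400 = 80 flares.

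**Model.** Nobody truly changes. Observed score = fixed true value + independent error at each visit. Anchor = category at visit 2 above category at visit 1. Outcome = visit 2 − visit 1. Each scenario has 400,000 simulated patients. Reliability, score distributions, error correlations and every boundary except DAPSA 4 are assumptions.

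**(a) Scale-free score, SD 1, test-retest correlation R = 0.70-0.95, one to three boundaries at population percentiles.** Smallest detectable change (SDC) = 1.96 × √2 × √(1 − R). For R = 0.80 this is 1.96 × 1.414 × 0.447 = 1.24 SD. Five equal independent items give an item-total correlation of change of 1/√5 = 0.447. Selected scenarios:

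| Boundaries (percentiles) | R | Anchor fires | AUC, same score | AUC, item (r = 0.447) | Change exceeded by 75% of 'flares' (SD) | SDC (SD) |
|---|---|---|---|---|---|---|
| 20 | 0.80 | 7.1% | 0.88 | 0.67 | 0.49 | 1.24 |
| 20 | 0.95 | 3.6% | 0.87 | 0.66 | 0.24 | 0.62 |
| 33, 67 | 0.80 | 17.4% | 0.92 | 0.68 | 0.46 | 1.24 |
| 20, 50, 80 | 0.70 | 25.9% | 0.95 | 0.69 | 0.53 | 1.52 |
| 20, 50, 80 | 0.80 | 22.4% | 0.94 | 0.69 | 0.45 | 1.24 |
| 20, 50, 80 | 0.95 | 12.2% | 0.90 | 0.68 | 0.24 | 0.62 |

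- False firing over all scenarios is 3.6-25.9%, or 0.036 × 400 = 14 to 0.259 × 400 = 104 patients. With three boundaries and R = 0.80 it is 0.224 × 400 = 90, against 80 expected flares.
- Same-score AUC is 0.87-0.95. At the Youden cutoff, sensitivity is 0.91-0.94 and specificity 0.69-0.83.
- Item AUC is about 0.58 at an item-total correlation of 0.2 and 0.76-0.81 at 0.7.
- An outcome whose error is independent of the anchor has AUC 0.50.

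**(b) DAPSA-like sum of five items, test-retest 0.82-0.99, error correlation between items 0 or 0.5.**

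- Boundary 4 alone: fires in 2.8-9.3%; DAPSA-change AUC 0.80-0.82.
- Boundary 4 with two assumed boundaries (10/20 or 14/28): fires in 5.9-24.1%; AUC 0.87-0.93.
- Pain and PGA: AUC 0.69-0.84.
- A patient-reported score outside the sum: 0.50 with independent errors, 0.71-0.76 if day-to-day error is shared (correlation 0.5).

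**(c) True flares added.** With an assumed 10-point rise in 20% of patients, same-score AUC is 0.81-0.94, and about 44-69% of category rises come from patients without a flare.

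**(d) Minimum-change rule.** In model (a), also requiring the rise to exceed the SDC cuts false firing from 4-26% to 0.5-2.4%. The same-score AUC then goes up to 0.99 or more. The rule reduces noise firing and leaves the circularity.

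**The case against.** **Reach.** A reader might infer that Table 3 as a whole produces spurious flare cutoffs. The documents do not support that. Only two of seven rows use category change and both are sensitivity analyses. Treatment intensification, the GRAPPA questionnaire and the three single-question rows do not use it. This objection stands and limits the point.

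**Accuracy of the components.** A reader might also infer near-perfect accuracy wherever a component appears. The figures do not show it: pain and PGA reach 0.58-0.84, and only same-score cells reach 0.80-0.95. This stands too.

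**Are the cells planned?** The body of Table 3 has no entries in the text available, so the same-score cells cannot be confirmed as planned. Obtaining cutoffs names all scores and excludes none, so the plan should say.

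**Existing safeguards.** Physicians complete their form without seeing the patient's, and composite scores are not calculated in the CRF. Both govern form-filling; neither separates a computed anchor from a computed outcome. The plan analyses patients with very high initial values separately, which largely meets the top-category concern, although it does not define very high. It does nothing for patients just below a boundary.

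**Zero change is not the study.** True: flares are expected, and flare visits are encouraged. But the same-score AUC barely moves when true flares are added (part c).

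**Kappa and the admitted lack of a gold standard.** Kappa between definitions could expose a noisy anchor. It would not alter the accuracy or cutoff reported in a circular cell. Conceding that every standard is partial does not help where the standard is the outcome itself.

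**Conclusion.** The point holds for the same-score cells of the DAPSA and PASDAS category-change rows and, more weakly, for pain and PGA in the DAPSA row. With no true flare, same-score AUC is about 0.80-0.95 and component AUC about 0.58-0.84, so these cells cannot serve as a sensitivity check on treatment intensification.

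The size rests on assumed test-retest reliability (0.70-0.95 in the scale-free model, 0.82-0.99 in the DAPSA-like one), assumed score distributions and error correlations, and assumed boundaries other than DAPSA 4. The direction follows from building anchor and outcome from the same two values. The 75%-rule change lies below the SDC in every tabulated scenario. That is a property of the model, because the documents report no measurement error. Which columns overlap with PASDAS cannot be settled from the documents. No main flare cutoff is affected.

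**What to change.** In Table 3 and the accompanying text:

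- Omit the cells where the column is the anchor score or one of its components, or label them non-informative and derive no cutoff from them. In the DAPSA row these are DAPSA/c-DAPSA, pain and PGA. In the PASDAS row they are PASDAS and whichever columns the sponsor identifies as its items.
- Keep the remaining columns, with a note that day-to-day error shared between patient-reported scores may still inflate accuracy.
- State that the separate analysis of very high initial values covers patients starting in the top category, who cannot rise.
- Optionally, repeat the two rows counting only rises above a prespecified measurement-error margin, and say that this lowers false firing without curing the circularity. Taking the margin from patients who answer 'the same' on the MCID question is debatable: it ties these rows to another Table 3 anchor, and visits 1-6 months apart are not a retest.

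The cost is revised wording and a few lost sensitivity cells. No new data are needed for the first three changes.
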